9.4 Storage

Blood and tumor samples collected for any studies performed in this protocol, and any other components from the processed cells, may be stored indefinitely to research scientific questions related to cancer and/or study drugs. The subject retains the right to have the sample material destroyed at any time by contacting the principal investigator.

9.5 Plan for Communication of Samples and Data

9.6 Plan for Communication of Collaborating Sites

Communication between centers will be critical in this trial. Prior to consent of the subject, the NMTRC research coordinator will be contacted (via e-mail). If a spot is available at the time, the potential subject will undergo consent and completion of all required screening procedures and certification of all inclusion and exclusion criteria by the Investigator. If the subject fits all enrollment criteria, the site will again contact the coordinator at the NMTRC who will notify TGen, Ashion, Spectrum Health, and the Pediatric Oncology Translational Research Laboratory in preparation for collection and processing of tissue sample. The research coordinator at NMTRC will organize the convening of members of the tumor board for discussion of the current case once the full report is available. In addition, a study enrollment form will be faxed to the coordinator at NMTRC, a unique subject identifier will be assigned and the enrollment form will be sent back to the participating site. The NMTRC will contact all sites via e-mail if the study enrollment is on hold or closed at any time.

Subject samples will be collected at each institution and follow the flow chart above. Once the reports are generated they will be sent to NMTRC/[name]. The Principal Investigator enrolling the patient will prepare a tumor board presentation. The presentation and reports will be sent to all tumor board members by the NMTRC coordinator. There will be a meeting of the tumor board within 4 days of receiving the report to decide on the treatment plan recommendation. The recommendation will be reviewed in depth for safety by the Pharmacist. The treatment plan and memo will be discussed with the subject and their parents and upon their signed agreement the treatment will begin within 1 week of the discussion with parents.

Each site will also participate in a 1 hour monthly video or teleconference meeting to review study progress and subjects currently enrolled. There will also be a yearly face-face study committee meeting hosted by a member institution.

10 ADVERSE EVENT REPORTING

10.1 Definitions

10.1.1 Adverse Event

An **adverse event** is any untoward medical occurrence in a subject or clinical investigation subject administered a pharmaceutical product and which does not necessarily have to have a causal relationship with this treatment. An adverse event can therefore be any unfavorable and unintended sign (including an abnormal laboratory finding, for example), symptom, or disease temporally associated with the use of a medicinal product, whether or not considered related to the medicinal product.

An untoward medical event which occurs outside the period of follow-up as defined in the protocol will not be considered an adverse event unless related to study drug. Worsening of a medical condition for which the efficacy of the study drug is being evaluated will not be considered an adverse event.

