3.3 Safety Evaluations

The principal investigator and the study chairs will evaluate reported serious adverse events and other toxicities in real time. Study chair and PI meetings will occur at least monthly. The principal investigator will meet with the clinical research team at frequent and regularly scheduled intervals to determine treatment modifications and treatment based toxicities.

Any safety concern or new information that might affect either the safety or the ethical conduct of this trial will be immediately forwarded to the study chairs in written form. The NMTRC will be responsible for informing the central IRB and DSMB. If trends in toxicities are noted or stopping rules are met, the study chair will temporarily suspend enrollment while reviewing the episodes with the DSMB. The DSMB will convene every 6 months for evaluation of all safety data.

Study will be on hold for safety monitoring by DSMB review when:

1. Any deaths deemed related to the study drug by the treating PI while on study or occurring less than 30 days after medications ended or 2 serious adverse events possibly related to protocol within 60 days.
2. Any other reason that the NMTRC feels it is in the best safety interest of the subjects.

Subjects will be required to either come off study or be dose reduced per treating physician standard of care if one of the following toxicities related to treatment regimen occurs. Toxicity will be graded according to the NCI-Common Terminology Criteria for Adverse Events (CTCAE v4.0).

Non-Hematologic toxicity:

- ≥Grade 3 non-hematological toxicity not resolved to <Grade 2 or baseline within 2 weeks excluding nausea, vomiting, anorexia, hypertension, electrolyte abnormalities corrected with oral supplementation.

Hematologic toxicity:

- Grade 4 neutropenia lasting ≥14 days;
- Grade 4 neutropenia with Grade 4 infection

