10.1.3 Serious Adverse Event

A ***serious adverse event*** is any untoward medical occurrence that:

- Results in death
- Is life-threatening (an event in which the subject was at risk of death at the time of the event; it does not refer to an event which hypothetically might have caused death if it were more severe)
- Requires in-patient hospitalization or prolongation of existing hospitalization
- Results in persistent or significant disability/incapacity
- Results in a congenital anomaly or birth defect
- Other important medical events that may not be immediately life-threatening or result in death or hospitalization but may jeopardize the subject or may require intervention to prevent one of the other outcomes listed above. Examples of such events are intensive treatment in an emergency room for allergic bronchospasm; blood dyscrasias or convulsions that do not result in hospitalization; or development of drug dependency or drug abuse.

The term “severe” is often used to describe the intensity (severity) of an event; the event itself may be of relatively minor medical significance (such as a severe headache). This is not the same as “serious”, which is based on subject/event outcome or action criteria usually associated with events that pose a threat to a subject’s life or functioning.

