10.1.5 Expedited Reporting of Serious Adverse Events

All fatal or life-threatening adverse events must be reported to the NMTRC immediately by telephone, fax, or e-mail within 24 hours of knowledge of the event. If full information is not known, additional follow-up by the Investigator will be required.

All other serious adverse events that are related and unexpected (not listed in the relevant appendices) which occur any time after the subject has been consented up to 30 days after the last dose of treatment, and are possibly, probably, or definitely related to the research must be reported to the study chair and appropriate regulatory authorities (local IRB and FDA if required) within 7 days of notification of the event.

The Investigator must report all serious adverse events reported to regulatory authorities in an expedited manner to the local IRB or IEC. All serious adverse events must be followed until resolution or stabilization. Unanticipated problems involving risk to subjects or others, serious adverse events related to participation in the study, and all volunteer deaths related to participation in the study should be promptly reported to the NMTRC.

NMTRC Reporting Contact

Please report all expedited reports to:

[name] and [name]
NMTRC
[contact]
E-Mail: [contact]
E-Mail: [contact]

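### Section 10.1.1 excludes worsening of the studied tumor from adverse events even when the treatment is suspected; this conflicts with 10.1.3 and, read literally, takes such events out of the 24-hour report

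*Combined protocol and SAP*

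**What the plan says.** Section 10.1.1 starts from a broad definition that includes unfavorable events "whether or not considered related to the medicinal product". It then makes two exclusions. An event outside the follow-up period "will not be considered an adverse event unless related to study drug". The next sentence reads: "Worsening of a medical condition for which the efficacy of the study drug is being evaluated will not be considered an adverse event". The first exclusion keeps drug-related events in. The second does not.

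Section 10.1.3 says that a serious adverse event "is any untoward medical occurrence that" meets one of the listed outcomes, with death and threat to life among them. It is not worded as a subset of the adverse events in 10.1.1, and it has no disease-worsening exclusion.

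The expedited rule in 10.1.5 is worded for adverse events: "All fatal or life-threatening adverse events must be reported to the NMTRC immediately by telephone, fax, or e-mail within 24 hours". Later in the same section, without using that term for deaths, it says that "all volunteer deaths related to participation in the study should be promptly reported to the NMTRC".

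The study hold in 3.3 has two numerical triggers. One is "Any deaths deemed related to the study drug by the treating PI while on study" or less than 30 days after medications ended. The other is 2 SAEs possibly related to the protocol within 60 days.

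**The concern.** Leaving ordinary tumor progression out of adverse event reporting is sensible in this population, because progression is frequent and is already an efficacy outcome. The difficulty is that the exclusion turns on what happened (the tumor got worse) and ignores the suspected cause. Bleeding or swelling in a brain tumor, or abrupt growth after a new combination starts, can be classed as worsening of the studied condition even when the investigator suspects the drugs.

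Evaluating the safety of tumor-board regimens is a stated secondary objective (2.2). Section 3.1.1 allows up to 4 agents together, and 3.1.2 provides for combinations with no combination data. Stratum 2 plans 50 subjects with brain tumors. A harm that shows itself as tumor worsening is therefore one that the safety data should be able to detect. The efficacy data do not fill the gap: progressive disease in 7.3 rests on measurements, new lesions, marrow or MIBG/PET findings, and carries no judgement of relatedness.

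**Working it through.** No calculation applies, because the point depends on no sample size, power or event figure. The check follows one event through each rule: serious tumor worsening that the investigator suspects the regimen caused.

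| Rule | Term it is worded for | Result if 10.1.1 is read literally |
|---|---|---|
| 10.1.3, SAE definition | any untoward occurrence | Event is an SAE |
| 10.1.4, source documents and case report form | adverse event | Not captured |
| 10.1.5, 24-hour report | fatal or life-threatening adverse event | Not reached |
| 10.1.5, 7-day report | other SAEs, related and unexpected | Reached if the 10.1.3 wording governs and the event is unexpected |
| 10.1.5, prompt report | related SAEs; related deaths | Related deaths reached; non-fatal events reached if 10.1.3 governs |
| 10.1.6.2, attribution | adverse event | No attribution step prescribed |
| Synopsis, safety measures | reported adverse events | Not tabulated as an adverse event |
| 3.3, first hold trigger | death the treating investigator deems drug-related | Reached |
| 3.3, second hold trigger | 2 possibly related SAEs in 60 days | Depends on whether an SAE must first be an adverse event |

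Four things follow.

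1. **The definitions conflict.** A fatal worsening is an SAE under 10.1.3 and not an adverse event under 10.1.1. No text says which section governs.

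2. **The deadline changes.** The event misses the 24-hour sentence. It may fall to the 7-day rule, a difference of up to 7 − 1 = 6 days, or to the prompt-report duty, which sets no time limit.

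3. **On the case report form, the exclusion can bite only on related events.** Section 10.1.4 asks for Grade 3 or higher events that are both related and unexpected. Unrelated progression is already filtered out by that condition, so all that the exclusion can add is to remove worsening that is related.

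4. **The hold count is open to two readings.** If 10.1.3 stands alone, a possibly related non-fatal serious worsening counts toward the two. If an SAE must first be an adverse event, it does not. With a threshold of two, one such event plus one other SAE in the window gives a count of 2 on the first reading and 1 on the second. The hold then fires on one reading and not on the other.

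**The case against.** The strongest reply is that the natural meaning of the sentence is disease progression as 7.3 measures it. Such progression is captured through progression-free survival and as an off-therapy reason in 11.1. Nothing obliges an investigator to class drug-suspected bleeding or swelling as worsening of the tumor, since it also fits the general definition as an unfavorable and unintended sign. Other safeguards remain: the 7-day and prompt-report duties in 10.1.5, and in 3.3 the real-time review of SAEs and other toxicities, the immediate written forwarding of safety concerns to the study chairs, and the power to hold the study for any other safety reason.

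Much of this stands. It rules out two stronger conclusions that a reader might draw.

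- *That treatment-caused deaths escape the study hold.* They do not. The first trigger in 3.3 covers any death the treating investigator deems drug-related and never uses the term adverse event, so 10.1.1 cannot switch it off. An indirect weakness remains: the trigger needs a relatedness judgement, and 10.1.6.2 prescribes one only for adverse events. That is not an exclusion.
- *That such events leave expedited reporting altogether.* They do not. Related deaths keep the prompt-report duty, and an event that is an SAE under 10.1.3 can still reach the 7-day rule.

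The reply does not remove the conflict. It relies on each site reading a limit into a sentence that has none, directly after a sentence where that limit is written out. Sites can reasonably differ, and the documents do not settle who is right.

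**Conclusion.** The point holds as a defect of definition. Read literally, 10.1.1 removes suspected drug-related fatal or life-threatening tumor worsening from the 24-hour report, adverse event capture, prescribed attribution and the adverse event tables, in conflict with 10.1.3. For non-fatal serious worsening, loss from the two-SAE hold count is one possible reading and not a certain one. Deaths deemed drug-related still trigger the hold and must still be promptly reported.

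No count of affected events can be given, because the documents state neither how often tumors are expected to worsen on treatment nor how often the drugs would be suspected. The conclusion does not need such a count. It assumes only that some sites will apply the sentence as written.

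**What to change.** Add to the disease-worsening sentence in 10.1.1: *unless considered at least possibly related to the treatment regimen*. This keeps ordinary progression out and restores only suspected drug-related worsening, using the *possible* category that 10.1.6.2 already defines.

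Reconcile 10.1.1, 10.1.3, 10.1.5 and 3.3 so that all four use one definition, and state whether an SAE must first be an adverse event. The reporting deadlines and the hold thresholds need not change.

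The cost is one clause, a wording check across four sections, and a few more adverse event and SAE reports.

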10.1.2 Unexpected Adverse Event

An **unexpected adverse event** is one for which the nature or severity of the event is not consistent with the applicable product information as outlined in package insert filed with the FDA.

10.1.3 Serious Adverse Event

A ***serious adverse event*** is any untoward medical occurrence that:

- Results in death
- Is life-threatening (an event in which the subject was at risk of death at the time of the event; it does not refer to an event which hypothetically might have caused death if it were more severe)
- Requires in-patient hospitalization or prolongation of existing hospitalization
- Results in persistent or significant disability/incapacity
- Results in a congenital anomaly or birth defect
- Other important medical events that may not be immediately life-threatening or result in death or hospitalization but may jeopardize the subject or may require intervention to prevent one of the other outcomes listed above. Examples of such events are intensive treatment in an emergency room for allergic bronchospasm; blood dyscrasias or convulsions that do not result in hospitalization; or development of drug dependency or drug abuse.

The term “severe” is often used to describe the intensity (severity) of an event; the event itself may be of relatively minor medical significance (such as a severe headache). This is not the same as “serious”, which is based on subject/event outcome or action criteria usually associated with events that pose a threat to a subject’s life or functioning.

10.1.4 Documenting Adverse Events

The Investigator should elicit information regarding the occurrence of adverse events through open-ended questioning of the subject, physical examination and review of laboratory results.

All adverse events, whether serious or not, will be described in the source documents and Grade 3 or higher (per CTCAE 4.0) related and unexpected adverse events that occur while on study should be captured on the adverse event case report form. All Baseline AE’s will be captured on a separate baseline Adverse event case report form. All Grade 3 or higher related and unexpected new events, as well as those that worsen in intensity or frequency relative to baseline, which occur after administration of study drug through the period of protocol-specified follow-up, must be captured.

Information to be reported in the description of each adverse event includes:

- A medical diagnosis of the event (if a medical diagnosis cannot be determined, a description of each sign or symptom characterizing the event should be recorded)
- The date of onset of the event and relatedness to treatment regimen.
- The date of resolution of the event and whether the event is serious or not
- Action taken; drug treatment required; non-drug treatment required; hospitalization or prolongation of hospitalization required; diagnostic procedure performed; subject discontinued from the study
- Outcome: complete recovery or return to baseline; unknown/lost to follow-up; adverse event persisting; subject died (notify the NMTRC immediately)

Adverse events will be collected for 30 days following the last treatment or until a new treatment is started. Suspected study drug-related toxicity at the 30 day follow-up visit must continue to be followed until resolution to baseline or \leq Grade 2 or stabilization of the event.

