	
targets and will be performed after cycle 2, then after every other cycle.
 
 • A subject will be defined as a responder if CR/PR is observed at any time of the treatment • Clinical response will be seen if stable disease and decrease in tumor markers by $\geq 50\%$ or CR of bone marrow. • Time to progression, defined as the period from the start of the treatment until the criteria for progression are met taking as reference the screening measurements • Comparisons of ORR and PFS for the first and second cohorts of 100 patients (i.e., those who enroll prior to versus after the implementation of Amendment 3.0, respectively) will be performed. 
Safety Measures: Secondary objectives
 
 • Safety analysis will be conducted on all subjects who have received at least one dose of therapy, and will include the frequency of all reported adverse events and laboratory abnormalities as well as frequency of dose interruptions, dose reductions and treatment discontinuation.
STATISTICS/SAMPLE SIZE ESTIMATE	
200 evaluable subjects
 
Patients who enroll following implementation of Amendment 3.0 (second cohort of 100 patients) will have their tumor biopsies analyzed using an updated Drug Prediction Report (Appendix III). Overall Response Rate (ORR) and Progression Free Survival (PFS) for this group will be compared to those of the first 100 patients who received treatment based upon the original Drug Prediciton Report and Pharmacopeia Library.

TABLE OF PROCEDURES AND ASSESSMENTS

Procedure	Screening	Cycle 1 Day 1	Cycle 1 Day 8	Cycle 1 Day 15	Cycle 1 Day 22 (if applicable)	Subsequent Cycles Day 1	Off Therapy/ 30 Day Follow-up
Informed consent	X						
Demographics	X						
Medical history	X	X	X	X	X	X	
Baseline Symptom Form	X	X					
Concurrent meds	X	X				X	X
Physical exam	X	X	X	X	X	X	X
Vital signs	X	X	X	X	X	X	X
Height	X	X				X	
Weight	X	X				X	X
Karnofsky or Lansky play score	X	X		X		X	X
CBC w/diff,	X	X	X	X	X	X	X
Serum chemistry *	X	X		X		X	X
Tumor Markers **	X	X				X	X
Adverse events			X	X	X	X	X
Surgical resection &/or diagnostic biopsy	X						
MRI or CT***	X						
MIBG/PET ***	X						
Bone Marrow (any subject suspected to have BM disease) ^	X						
B-HCG	X						
EKG (as indicated)		X					

* Serum electrolytes, BUN, Creatinine, Bilirubin, ALT, AST

**LDH and/or Specific Tumor Markers for defined disease (if available)

***Type of scan as indicated for disease type

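### On-study AE form entry is required only for Grade 3 or higher events that are both related and unexpected, so the planned AE frequencies will understate Grade 3+ toxicity

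*Combined protocol and SAP*

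**What the plan says.** Section 10.1.4 sets two levels of recording. At the first, "All adverse events, whether serious or not, will be described in the source documents". At the second, the AE case report form, the requirement is narrower: "Grade 3 or higher (per CTCAE 4.0) related and unexpected adverse events that occur while on study should be captured". The section repeats this condition for new events after study drug and then adds "as well as those that worsen in intensity or frequency relative to baseline", without saying which events *those* are. Baseline events go on a form of their own.

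Section 10.1.2 calls an event unexpected when its nature or severity is "not consistent with the applicable product information as outlined in package insert filed with the FDA". A toxicity that matches the label in both respects is therefore expected.

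The only description of a safety analysis is in the Synopsis, under Criteria for Evaluation, Safety Measures. It covers everyone who received at least one dose and "will include the frequency of all reported adverse events and laboratory abnormalities", "as well as frequency of dose interruptions, dose reductions and treatment discontinuation". Sections 12.3 and 12.4, which hold the analysis plan, do not mention AEs. Section 2.2 makes the safety of tumor-board treatment plans a secondary objective.

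**The concern.** The analysis is described as a frequency of AEs, but the form that would supply it filters events on attribution and on expectedness before they are entered. Both filters bear on what this trial is meant to learn. Section 1.2 names toxicity from novel combinations as a concern, and Section 3.1.1 allows up to four agents together. The test in Section 10.1.2 looks at nature and severity, not at how often an event occurs. If a combination makes a labelled toxicity more common, each occurrence at labelled severity is still expected, and none has to be entered.

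At stake is how the AE table can be read. A short table could be taken as good tolerability when the entry rule explains it. Under Section 12.2 the DSMB receives database summaries that include AE reports, so summaries of non-serious events may carry the same limit.

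**Working it through.** No stated figure can be reproduced: the documents give no AE rate and no share of events at labelled severity. The check is to run types of event through the rules. Inputs are 10.1.2 (expectedness), 10.1.3 (seriousness), 10.1.4 (form entry), 10.1.5 (expedited reports) and the synopsis safety analysis.

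| Event after start of study drug | AE form entry required by 10.1.4? | Reporting route in 10.1.5? |
|---|---|---|
| New, non-serious, Grade 3+, related, beyond label in nature or severity | Yes | None needed |
| New, non-serious, Grade 3+, related, at labelled nature and severity | No: not unexpected | No: not serious |
| New, non-serious, Grade 3+, judged unrelated | No: not related | No: not serious |
| Serious and related, at labelled nature and severity | No: not unexpected | Yes, as a serious event related to participation |
| Fatal or life-threatening, any attribution | Only if related and unexpected | Yes |

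The second and third rows are the gap. Four further steps test it.

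1. *The worsening clause.* Read narrowly, *those* means Grade 3+ related and unexpected events that worsen. Read broadly, it means any baseline event that worsens. Neither reading reaches an event that was absent at baseline, so the gap for new-onset events does not depend on the choice.

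2. *Seriousness.* Section 10.1.3 narrows the gap somewhat, because important medical events such as "blood dyscrasias or convulsions that do not result in hospitalization" count as serious. Section 10.1.5 does not say, however, that its reports feed the AE table.

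3. *Other data.* The synopsis also tabulates laboratory abnormalities, dose interruptions, dose reductions and discontinuations. Section 6.2 puts all concomitant medications and treatments on a case report form and names anti-emetics among them. Section 11.1 lists an adverse event as a reason for stopping therapy. A labelled cytopenia may thus appear as a laboratory finding, and treated nausea as a concomitant medication. These are indirect traces; none is a count of patients with the event by grade.

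4. *The word* reported *in the synopsis.* If it means entered on the form, the table's label is correct by definition, but the second and third rows are still absent from it.

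The direction follows from the rule: leaving eligible events out can only lower the counts. The size would need the true rate of such events, the share at labelled severity and the share judged unrelated. None of these is in the documents.

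**The case against.** The best case against the point has four parts.

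*The rule is a minimum.* Section 10.1.4 does not bar further entry, all events are in source documents, and Sections 12.1 and 13.3 provide for checks of forms against source. This stands. It is why the point says that entry is not required, and not that the events are lost. Those checks test whether form entries are correct and complete; they do not widen the entry rule.

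*The phrase could mean related events plus unexpected events.* On that reading labelled related toxicity would be entered, and only events both unrelated and expected would be left out. Some text suggests wider capture: the fields for relatedness and seriousness and the unqualified 30-day collection in 10.1.4, grading from Grade 2 in 10.1.6.1, and the unrelated categories in 10.1.6.2. Yet Section 10.1.5 uses the same phrase jointly, in "All other serious adverse events that are related and unexpected (not listed in the relevant appendices", and the joint reading is the natural one. The other text sits badly with the rule but does not change it.

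*Selective capture can be reasonable* in a feasibility trial of approved and over-the-counter agents where safety is secondary. That also stands, provided the table is labelled accordingly.

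*No conclusion is said to rest on this table alone.* That is correct. The point is about what the table can support.

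A reader might infer more: that serious toxicity goes unseen, or that patient oversight fails. The documents do not support this. Section 10.1.5 covers fatal or life-threatening events and serious events related to participation, and Section 3.3 provides for real-time review of SAEs and other toxicities. Nor would full capture by itself show that combinations raise toxicity, since the documents give no reference rate.

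**Conclusion.** The point holds in this form and should be fixed. Followed as written, Section 10.1.4 does not require form entry of new-onset, non-serious Grade 3 or higher events that are at labelled severity or judged unrelated. The AE frequencies planned in the synopsis will then understate Grade 3+ toxicity by an unknown amount.

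This rests on three assumptions: sites enter what is required and little more; the phrase is read jointly; and *unexpected* follows Section 10.1.2. Section 10.1.5 uses a different reference, listing in the appendices, but only for expedited SAE reports. Appendix III as shown lists product names without side effects. Applied literally to 10.1.4, that reference would bring labelled related events into the form and leave the gap for unrelated ones.

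**What to change.** Amend Section 10.1.4 prospectively:

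- Enter every Grade 3 or higher AE and every SAE on the AE form, with attribution and expectedness as recorded fields and not as conditions for entry.
- State which events the worsening clause refers to.
- Tabulate all-cause and related events by patient.
- Label tables for subjects treated before the change as limited capture.

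If the present rule is kept, label the synopsis AE table as restricted to the events that 10.1.4 requires, and draw no overall tolerability conclusion from that table alone.

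The amendment costs protocol and form wording and extra data entry. It needs no new visit or test, because events are already described in source documents (10.1.4), graded from Grade 2 (10.1.6.1) and assessed for attribution (10.1.6.2). Reported frequencies will rise and will not be comparable before and after the change. No planned comparison is lost: the cohort comparisons in the synopsis and Section 8 are of response rate and PFS. Retrieving earlier events from source, including those of the 100 subjects already enrolled at Amendment 3.0 (Section 8), would cost more and is optional. Relabelling costs wording only, but gives up an overall tolerability statement from the AE table.
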